## 6. STUDY ASSESSMENTS AND PROCEDURES

**Table 1 Time and Events Table**

Procedures	Screening  ( ≤ 4 weeks prior to dosing)  Visit 1	Baseline (Day 0) Visit 2	First Year (Week)  Visit 3~6				Second year (Week)  Visit 7~10				third Year to Fourth year (Week)  Visit 11~18				Last Year (Week)  Visit 19-22				Withdraw  (Week off treatment)
			12 ±6 d	24 ±6 d	36 ±6 d	48 ±6 d	60 ±6 d	72 ±6 d	84 ±6 d	96 ±6 d	108 ±6d	120 ±6d	132 ±6d	144 ±6d	204 ±6d	216 ±6d	228 ±6d	240 ±6d	
			156 ±6d	168 ±6d	180 ±6d	192 ±6d													
Written informed consent	√																		
Subject demography 	√																		
Medical history	√ 	√ 																	
Inclusion/exclusion criteria	√																		
Concomitant medication 		√	√	√	√	√	√	√	√	√	√	√	√	√	√	√	√	√	√
Physical examination 	√	√	√	√	√	√	√	√	√	√	√	√	√	√	√	√	√	√	√
Vital signs 	√	√	√	√	√	√	√	√	√	√	√	√	√	√	√	√	√	√	√
Adverse events		√	√	√	√	√	√	√	√	√	√	√	√	√	√	√	√	√	√
Serious adverse events		√	√	√	√	√	√	√	√	√	√	√	√	√	√	√	√	√	√
Laboratory assessments																			
Haematology	√	√		√		√		√		√		√		√		√		√	√
Chemistry(Liver & Renal function, electrolyte(phosphate and calcium inclusive))	√	√	√	√	√	√	√	√	√	√	√	√	√	√	√	√	√	√	√
Pregnancy test 	√	√	√	√	√	√	√	√	√	√	√	√	√	√	√	√	√	√	√
HAV/HCV/HDV/HEV/HIV / ANA	√																		
B-ultrasound 	√	√	√	√	√	√	√	√	√	√	√	√	√	√	√	√	√	√	√

Fibroscan	√	√	√	√	√	√	√	√	√	√	√	√	√	√	√	√	√	√	√
AFP	√	√	√	√	√	√	√	√	√	√	√	√	√	√	√	√	√	√	√
Urinalysis 	√	√	√	√	√	√	√	√	√	√	√	√	√	√	√	√	√	√	√
Prothrombin time and INR	√	√	√	√	√	√	√	√	√	√	√	√	√	√	√	√	√	√	√
HBV DNA 	√	√	√	√	√	√	√	√	√	√	√	√	√	√	√	√	√	√	√
HBeAg/Anti-HBe	√	√	√	√	√	√	√	√	√	√	√	√	√	√	√	√	√	√	√
HBsAg/Anti-HBs	√	√	√	√	√	√	√	√	√	√	√	√	√	√	√	√	√	√	√
Genotyping 		√																	
Genotypic analysis 							√	√	√	√		√		√		√		√	√
Investigational product																			
Study drug dispensed and reconciliation of drug supply 		√	√	√	√	√	√	√	√	√	√	√	√	√	√	√	√	√	√
Liver biopsy	√															√			
Serum and plasma storage	√	√	√	√	√	√	√	√	√	√	√	√	√	√	√	√	√	√	√

- 1 All results to be obtained before baseline visit.
- 2 No more than 6 days before or 6 days after the date scheduled based on the time from baseline visit not from the previous visit.
- 3 In the event of early study drug discontinuation, the evaluation should be performed in 12 weeks after discontinuation of study treatment.
- 4 Medical history will include any acute and chronic medical conditions including prior surgery, information related to hepatitis B history, any current and prior HBV medications, and previous HBV-related procedures.
- 5 Update any new medical conditions and/or concomitant medications that have occurred since study screening.
- 6 Concomitant medications including traditional Chinese medicines and/or herbal remedies.
- 7 At screening, a complete physical examination will be performed. For all following indicated visits, a brief physical examination will be performed.
- 8 Including blood pressure, pulse, respiratory rate and temperature.
- 9 Urine pregnancy test will be performed at screening, baseline and every 3 months after dosing.
- 10 HBV DNA will be tested using Roche COBAS Taqman HBV test(LLD 20 IU/mL).
- 11 Each study visit: All study medication to be collected and reconciled.

- 12 Liver biopsy will be done in 100 subjects in sites at baseline and week 216. Liver biopsy can be done at screening (Visit 1) or at baseline (Visit 2), at the discretion of investigator. Liver biopsy slides within 6 months prior to baseline can be accepted as baseline evaluation.
- 13 Tests will be performed at central lab
- 14 Demographic data includes birth date, gender and race
- 15 B ultrasound examination include liver, pancreas, spleen, gall bladder and kidney
- 16 Urinalysis: urine glucose, ketones, specific gravity, blood, pH and protein
- 17 Serum will be collected as scheduled for potential resistance surveillance. Genotypic analysis will be performed under the condition defined in protocol (see section 6.2.8)
- 18 Genotyping will be performed at central lab at screen

## 6.1. Critical Baseline Assessments

Prior to dispensing study medication on Day 1, the procedures listed in Table 1 must be performed and documented in the CRF.

The first dose of study medication will be administered at this visit, after all the study procedures have been completed. Subjects can be discharged immediately after dosing.

## 6.2. Efficacy

Samples for efficacy analysis will be collected at times outlined in Table 1. Collection and processing procedures for each type of sample will be detailed in the SPM.

### 6.2.1. Serum/Plasma Storage

Serum and plasma will be stored at the central laboratory and frozen at or below -20°C to allow possible evaluation of changes in laboratory markers of HBV infection (including resistance testing) observed during the course of the study.

### 6.2.2. Primary Endpoint

To determine the incidence of newly diagnosed HCC (from week 24 to week 240), the subject must meet one of the following criteria:

- A histological diagnosis of HCC (i.e. by biopsy or at post-mortem)
- In patients with nodules >2 cm, identification of typical HCC characteristics (hypervascular in the arterial phase with washout in the portal venous or delayed phases) by 4-phase multidetector CT scan or dynamic contrast-enhanced MRI
- In patients with nodules > 1 cm, , identification of typical HCC characteristics by both techniques (4-phase multidetector CT and dynamic contrast-enhanced MRI )

### 6.2.3. Clinical Endpoint

The cumulative incidence of disease progression during the study timepoints will be defined as the first occurrence of any one of the following criteria:

- an increase in Childs-Pugh score (as defined in section 11.1 Appendix 1) of 2 or more points from baseline.
- An increase in Childs-Pugh score of 2 or more points, solely based on laboratory parameters (i.e. bilirubin, prothrombin time and/or albumin), confirmed at two consecutive visits at least one month apart;
- spontaneous bacterial peritonitis (with proven sepsis);

- renal insufficiency defined as a decrease in creatinine clearance to  $\leq 50$  mL/minute confirmed on two occasions at least one week apart (calculated from serum creatinine concentration);
- bleeding gastric/oesophageal varices;
- hepatocellular carcinoma;
- liver-related death

#### **6.2.4. Virological Endpoint**

To evaluate the proportion of subjects with HBV DNA < 20 IU/mL and viral load change over time, HBV DNA level will be quantified using the Roche COBAS Taqman HBV test (LLD 20IU/mL) at times outlined in Table 1.

#### **6.2.5. Biochemical Endpoint**

To evaluate the biochemical response, ALT will be measured at times outlined in Table 1.

#### **6.2.6. Serological Endpoint**

To evaluate the serological response, HBeAg/anti-HBe and HBsAg/anti-HBs will be measured at times outlined in Table 1.

#### **6.2.7. Liver fibrosis endpoint**

Liver fibrosis will be assessed using non-invasive FibroScan in all study subjects, and by formal liver biopsy in a subset of study subjects.

To assess liver fibrosis changes non-invasively a liver stiffness measure (LSM) will be obtained for all patients by transient elastography using FibroScan (EchoSens) at times outlined in Table 1.

. The LSM result will be expressed as a median value of the total measurements in kiloPascal (kPa). Only subject examinations with at least 10 validated measurements, a success rate of at least 60%, and an interquartile range (IQR) of all validated measurements of less than 30% will be considered a reliable LSM measure. Mean changes of LSM at Week 48, Week 96, Week 144, Week 192 and Week 240 will be reported.

To evaluate the proportion of subjects who experience an improvement in histology at Week 216 a subset of study subjects (approximately 100 subjects) will undergo liver biopsies at times outlined in Table 1.

A single central pathologist will evaluate all baseline and final biopsy slides in a paired fashion and blinded to timing of biopsy. The baseline and end of treatment biopsies will be read at the same time. (See Appendix 3)

### 6.2.8. Resistance Surveillance

To evaluate the resistance (if identified) rate, genotypic analysis of the HBV polymerase gene will be performed on storage serum at times outlined in Table 1 using a central laboratory in the following situations:

- Subjects with HBV DNA  $\geq 20$  IU/mL at their last visit. (i.e. week 240 or last visit before withdrawal)
- Subjects with virological breakthrough, defined as HBV DNA level increase  $\geq 1$   $\log_{10}$  IU/mL above the treatment nadir (confirmed on two consecutive visits at least 1 month apart).
- Subjects have HBV DNA  $\geq 200$  IU/mL at week 48 and afterwards have  $\leq$  one log decrease in HBV DNA at two consecutive visits, confirmed by a third visit at least one month apart.

### 6.3. Safety

#### 6.3.1. On-Treatment ALT Flare, ALT Elevation With or Without Hepatic Dysfunction, and Post-Treatment Exacerbation of Hepatitis Management

##### DEFINITIONS

ALT FLARE	ALT Both $>2x$ baseline value and $>10x$ ULN	See Section 6.3.1.1
ALT ELEVATION With HEPATIC DYSFUNCTION	ALT Both $>2x$ nadir value and $>5x$ ULN with evidence of worsened hepatic function (e.g. Direct Bilirubin $>1.5$ mg/dL INR $\geq 1.7$ , or abnormal serum albumin $\leq 2.7$ )	See Section 6.3.1.1
ALT ELEVATION ALONE	ALT Both $>2x$ nadir value and $>5x$ ULN	See Section 6.3.1.2

#### 6.3.1.1. Management of ALT Flare or ALT Elevation With Hepatic Dysfunction in Subjects Receiving Study Medication

If laboratory results indicate **ALT Flare** or **ALT Elevation With Hepatic Dysfunction** the following is recommended:

Schedule the subject to return to the clinic as soon as possible (ideally within 3 days after initial laboratory results were drawn). During the visit, a clinical assessment of the subject will be performed. The assessment should include a physical examination and evaluation of the subject's mental status.

Check the following laboratory parameters: serum ALT and AST, alkaline phosphatase, total and direct bilirubin, INR, and serum albumin.

If the **ALT Flare** or **ALT Elevation With Hepatic Dysfunction** is confirmed, request the clinical laboratory to conduct reflex testing for plasma HBV DNA, serology for HBV (HBsAg, HBeAg, HBeAb, and HBsAb), HDV, HAV IgM, HCV, and HEV

Based on the results of the confirmatory tests, the following treatment modifications are recommended:

**Evidence of worsening HBV infection:**

- If Plasma HBV DNA is increasing ( $\geq 1$  log increase), the investigator should discuss initiation of additional therapy with the medical monitor.

**In the absence of evidence of worsening HBV infection:**

- If ALT levels are elevated (+/- direct bilirubin/INR/albumin) as above, the subject may remain on study medication and should be monitored with ALT and AST, alkaline phosphatase, total and direct bilirubin, INR, and serum albumin at least weekly until laboratory abnormalities return to baseline level.
- During monitoring, if the ALT values (+/- direct bilirubin/INR/albumin) are worsening or remain persistently abnormal or elevated after 4 weeks, the Investigator should discuss with the Medical Monitor regarding the monitoring schedule and whether the study drug should be discontinued.

For subjects with bridging fibrosis or cirrhosis, study drug discontinuation with treatment-free follow-up is to be avoided due to the potential risk of exacerbation of hepatitis in the setting of low hepatic reserve which could lead to decompensation. Subjects with bridging fibrosis or cirrhosis should be placed on commercially available HBV therapy following study drug discontinuation.

Subjects should be followed until laboratory parameters return to baseline up to a maximum of 6 months after the initial occurrence of the event.

**6.3.1.2. Increased monitoring for On-Treatment ALT Elevation Alone**

- In patients with confirmed **ALT Elevation Alone (both  $>2x$  nadir and also  $>5x$ ULN)** but have not reached **ALT Flare (Both ALT  $>2x$  baseline value and  $>10x$  ULN)** and do not have evidence of worsened hepatic function (e.g. Direct Bilirubin  $>1.5$ mg/dL INR  $\geq 1.7$ , or abnormal serum albumin  $\leq 2.7$ ) the subject may remain on study medication and should be monitored weekly until ALT levels return to baseline level. During monitoring, if after 4 weeks the ALT values remain stable but persistently abnormal, the Investigator should discuss with the Medical Monitor regarding the monitoring schedule.

If patients worsen to reach ALT Flare definition or ALT Elevation with hepatic dysfunction, manage as above in Section 6.3.1.1.

Subjects should be followed until laboratory parameters return to baseline up to a maximum of 6 months after the initial occurrence of the event.

### **6.3.1.3. Management of Exacerbation of Hepatitis in Subjects who have Discontinued Study Medication**

If laboratory results indicate **ALT Flare** or **ALT Elevation With Hepatic Dysfunction** and the subject is on no post-study therapy for HBV, the following is recommended:

- Schedule the subject to return to the clinic as soon as possible (ideally no later than 3 days after the initial laboratory values were drawn). During the visit, perform a clinical assessment of the subject.
- Check the following laboratory parameters: serum ALT and AST, alkaline phosphatase, total and direct bilirubin, INR, and albumin.
- If the **ALT Flare** or **ALT Elevation With Hepatic Dysfunction** is confirmed, request the clinical laboratory to conduct reflex testing for plasma HBV DNA, serology for HBV (HBsAg, HBeAg, HBeAb, and HBsAb), HDV, HAV IgM and HCV. If Plasma HBV DNA is increasing ( $\geq 1$  log increase), the investigator should consider immediate initiation of approved therapy.
- Subjects should be followed until laboratory parameters return to baseline up to a maximum of 6 months after the initial occurrence of the event.

Please refer to Appendix 4: Lactic Acidosis Guidelines for the recommend method for managing lactic acidosis.

### **6.3.2. Serum Creatinine Elevation**

Serum creatinine values  $\geq 0.5$  mg/dL above baseline should be confirmed by repeat testing within 3 calendar days of receipt of results.

For serum creatinine elevations  $\geq 0.5$  mg/dL above baseline, subjects may continue all study medication, but it is recommended that subjects be monitored weekly until the serum creatinine returns to the original baseline value or  $\leq 0.3$  mg/dL from baseline.

All study drugs should be permanently discontinued in the event that repeat testing of serum creatinine confirms  $>2.5$  mg/dL. The subject should be followed weekly until the serum creatinine reaches within 0.3 mg/dL of the baseline value.

### **6.3.3. Adverse Events**

The investigator or site staff will be responsible for detecting, documenting and reporting events that meet the definition of an AE or SAE.

### 6.3.3.1. Definition of an AE

Any untoward medical occurrence in a patient or clinical investigation subject, temporally associated with the use of a medicinal product, whether or not considered related to the medicinal product. Any noxious or unintended response to a medicinal product related to any dose should be considered an adverse drug reaction (ADR).

Note: An AE can therefore be any unfavorable and unintended sign (including an abnormal laboratory finding), symptom, or disease (new or exacerbated) temporally associated with the use of a medicinal product.

Events meeting the definition of an AE include:

- Exacerbation of a chronic or intermittent pre-existing condition including either an increase in frequency and/or intensity of the condition
- New conditions detected or diagnosed after study treatment administration even though it may have been present prior to the start of the study
- Signs, symptoms, or the clinical sequelae of a suspected interaction
- Signs, symptoms, or the clinical sequelae of a suspected overdose of either study treatment or a concomitant medication (overdose per se will not be reported as an AE/SAE) unless this is an intentional overdose taken with possible suicidal/self-harming intent. This should be reported regardless of sequelae.

“Lack of efficacy” or “failure of expected pharmacological action” per se will not be reported as an AE or SAE. However, the signs and symptoms and/or clinical sequelae resulting from lack of efficacy will be reported if they fulfil the definition of an AE or SAE.

The signs and symptoms and/or clinical sequelae resulting from lack of efficacy will be reported if they fulfill the definition of an AE or SAE. Also, “lack of efficacy” or “failure of expected pharmacological action” also constitutes an AE or SAE.

Events that **do not** meet the definition of an AE include:

- Medical or surgical procedure (e.g., endoscopy, appendectomy); the condition that leads to the procedure is an AE
- Situations where an untoward medical occurrence did not occur (social and/or convenience admission to a hospital)
- Anticipated day-to-day fluctuations of pre-existing disease(s) or condition(s) present or detected at the start of the study that do not worsen
- The disease/disorder being studied, or expected progression, signs, or symptoms of the disease/disorder being studied, unless more severe than expected for the subject’s condition

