#### **8.3.5.2. Safety Analyses**

Clinical safety observations will include: extent of exposure information, AEs, deaths, laboratory abnormalities and withdrawals from study. The safety data will be tabulated and, where appropriate, a Fisher's exact test comparing treatment groups will be run.

Extent of exposure to study drug data will be generated from the study drug administration page of CRF. Exposure data will be summarised by treatment group.

Adverse events will be assigned preferred terms and categorized into body systems according to the MedDRA classification of the World Health Organisation terminology. The proportion of subjects who experienced AEs will be calculated by dividing the number of subjects who experienced the AE during the treatment period by the number of

subjects evaluable for safety analysis. Adverse events will be summarised by treatment group, and by body system and event within each body system. The following summaries of AEs will be provided:

- All AEs.
- All treatment related AEs.
- All SAEs.
- All treatment related SAEs.
- All AEs leading to permanent discontinuation of study drug.
- All AEs leading to permanent discontinuation from the study.

All AEs that caused a change in dose or temporary interruption of study drug.

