7. STATISTICAL ANALYSIS

7.1 Subject screening, disposition and protocol deviations

The screening failure subjects and the reasons for screening failure will be summarized by the numbers and percentages. The percentages are based on the number of screening failure subjects.

The disposition of subjects will be summarized, including the numbers and percentages of subjects for the following categories: all enrolled subjects, subjects completed the study, subjects early discontinued from the study, subjects in the modified intent to treat population, subjects in the per-protocol population, and subjects in the safety analysis population. All percentages are based on the number of all enrolled subjects.

The primary reason for subject premature discontinuation from study will also be summarized. The reasons for discontinuation will include voluntarily discontinue participation, lost to follow-up, lack of efficacy, subjects with treatment interruptions of ≥ 28 consecutive days, adverse event, intercurrent illness, protocol violations, pregnancy, and other reason. A listing will be provided.

Major protocol deviations will be summarized and listed for mITT population. Subject counts and percentages will be displayed by the following deviation categories:

- Eligibility criteria not met
- Excluded medication, vaccine or device
- Assessment or time point completion
- Wrong study treatment/administration/dose

Major protocol deviations which results in the exclusion of the subject from PP population will be discussed, determined, and documented by study team before final database lock. A listing of subject disposition in analysis data sets will be provide.

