7.5.1 Adverse events

AEs will be classified into standardized medical terminology from the verbatim description (investigator term) using the Medical Dictionary for Regulatory Activities (MedDRA). Verbatim description and MedDRA level terms, including the system organ class, preferred term, and lower level term, for all AEs will be presented in the data listings. In table summaries, the denominator for percentages will be the number of subjects in the treatment group within the safety analysis population. AEs are coded according to (MedDRA) version 17.0.

TEAE is defined as AE occurred on or after the first dose date of study drug. TEAEs will be presented by system organ class and preferred term. The subject level incidence is only one occurrence of a preferred term/system organ class per subject. If a subject reports multiple AEs under the same preferred term, then the count of subject level incidences for that preferred term will only be incremented by one. If a subject reports multiple AEs under the same system organ class, then the count of subject level incidences for that system organ class will also only be incremented by one. System organ classes will be presented in descending order of total frequency of subject level occurrences. Within each system organ class, preferred terms are presented in the same descending order of total frequency of subject level occurrences.

An overall summary table of AE will be provided, including summaries of all AEs, all TEAEs, all treatment related TEAEs, all serious TEAEs, all treatment related serious TEAEs, all TEAEs leading to permanent discontinuation of study drug, all TEAEs leading to permanent discontinuation from the study, and all TEAEs that caused a change in dose or temporary interruption of study drug. Listings will be provided correspondingly.

All TEAEs and all serious TEAEs will be summarized by SOC and PT, and by intensity. All TEAEs will also be summarized by relationship to study drug.

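### Protocol 6.3.3.1 gives opposite rules, in consecutive paragraphs, on whether lack of efficacy is itself an adverse event, and nothing in the protocol or SAP says which one applies

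*Protocol*

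**What the plan says.** Protocol 6.3.3.1 deals with lack of efficacy in two consecutive paragraphs. The first says that lack of efficacy or failure of expected pharmacological action "per se will not be reported as an AE or SAE", and that only its clinical consequences are reported when they qualify. The second repeats that allowance ("The signs and symptoms and/or clinical sequelae resulting from lack of efficacy will be reported if they fulfill the definition of an AE or SAE") and then adds that lack of efficacy or failure of expected pharmacological action "also constitutes an AE or SAE".

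Protocol 6.3.3 leaves the application to the sites: "The investigator or site staff will be responsible for detecting, documenting and reporting events that meet the definition of an AE or SAE". The analyses take over whatever is reported. Protocol 8.3.5.2 states: "The proportion of subjects who experienced AEs will be calculated by dividing the number of subjects who experienced the AE during the treatment period". SAP 7.5.1 builds on the same term without redefining it: "TEAE is defined as AE occurred on or after the first dose date of study drug".

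**The concern.** The two paragraphs use the same terms and give opposite instructions. No condition, population or time window separates them, so a site cannot follow both. The case is also foreseeable here. The protocol defines virological breakthrough and inadequate response from Week 48 onward, and the SAP tabulates both as secondary endpoints.

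If sites resolve the conflict in different ways, the AE summaries will mix drug safety with treatment failure to an unknown degree, and a reader of the tables could not tell which rule produced a given count. Safety is part of the secondary objective, so these summaries are a planned result of the trial.

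**Working it through.** The plan states no figure to reproduce. The check is a comparison of texts, followed by simple arithmetic for scale.

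**1. Where the paragraphs agree and where they differ**

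| Situation | First paragraph | Second paragraph |
|---|---|---|
| Failure with signs, symptoms or sequelae that qualify as an AE or SAE | Reported | Reported |
| Failure as such, without such consequences | Not reported | An AE or SAE |

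The conflict is confined to the second row.

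**2. Does another section settle it?**

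- *Protocol 6.3.3.1, list of events that are not AEs.* It excludes "The disease/disorder being studied, or expected progression, signs, or symptoms of the disease/disorder being studied, unless more severe than expected for the subject"'s condition. This leans towards non-reporting, but it does not name lack of efficacy or override the second paragraph.
- *Protocol 6.3.6.* It excludes abnormal assessments associated with the underlying disease unless they are worse than expected. It leans the same way, with the same limit.
- *Protocol 6.3.3.2.* It defines seriousness, not whether lack of efficacy is an event.
- *Protocol 6.3.8 and 6.3.10.* They set collection periods and reporting times only.
- *SAP 7.1.* It says: "The reasons for discontinuation will include voluntarily discontinue participation, lost to follow-up, lack of efficacy", with adverse event as a further entry. This is a list of single primary reasons for leaving the study and does not define an AE.
- *SAP 7.5.1.* It has no rule on lack of efficacy.

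None of these sets precedence.

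**3. Which outputs are exposed?**

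- The all-AE, treatment-related and AE-leading-to-discontinuation summaries in Protocol 8.3.5.2 and SAP 7.5.1.
- The agreement between tables. Under the second paragraph, one failure could be a lack-of-efficacy withdrawal in the disposition table and also an AE leading to discontinuation in the safety table. Under the first, the failure as such could appear only in the disposition table.
- Serious AEs, to a lesser degree. The second paragraph names SAEs, but failure without sequelae would ordinarily meet no criterion in 6.3.3.2 other than medical judgement. Reporting within 24 hours follows only if the event is classed as serious.
- Not the primary endpoints. HCC and disease progression have their own definitions in Protocol 6.2.2 and 6.2.3 and SAP 5.1.

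**4. Scale**

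Input: 186 planned subjects (Protocol 4.1), all assumed to be in the safety population.

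One reclassified subject with no other AE: 1/186 = 0.0054, or 0.54 percentage points of the overall AE proportion.

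The documents give no failure rate. As an assumption only, suppose 1% to 10% of subjects had failure as such:

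- 0.01 × 186 = 1.86, about 2 subjects; 2/186 = 1.1 percentage points
- 0.10 × 186 = 18.6, about 19 subjects; 19/186 = 10.2 percentage points

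The row for the matching preferred term could move by these amounts between the two readings. The overall AE proportion moves that far only if none of these subjects has any other AE in 240 weeks, so for that proportion they are upper limits.

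**The case against.** The strongest reply is that this is an editorial slip with limited reach. Much of that stands:

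- **Single arm, pooled tables.** No comparison is planned and SAP 7.5.1 has no table by site, so inconsistent reporting between sites biases no planned contrast. It can still shift the pooled proportions.
- **The failures remain visible.** Virological breakthrough and unsatisfactory response are tabulated (SAP Tables 4.9.1 and 4.9.3) and the HBV DNA results of these patients are listed (SAP 7.4.3), whatever the AE coding. This makes the problem recoverable, but does not say what the AE tables should contain.
- **Site instructions may exist.** Protocol 6.3.10 places the method of recording and evaluating AEs in the Study Procedures Manual, which is not among the documents reviewed. Sites may therefore differ; the documents do not show that they will.

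Two stronger readings are tempting and are not supported. A reader might infer from SAP 7.1 that the first paragraph was intended, because lack of efficacy and adverse event are separate reasons for discontinuation. The same list also separates intercurrent illness from adverse event, although a new illness on treatment would be an AE under 6.3.3.1. Separate entries in a list of primary reasons therefore fit either paragraph. A reader might also infer that the second paragraph turns every breakthrough or unsatisfactory response into an AE or SAE. No text equates those virological definitions with lack of efficacy, and the exclusions for the underlying disease point the other way.

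**Conclusion.** The contradiction is real: two current, consecutive paragraphs give incompatible reporting rules, and neither the protocol nor the SAP resolves them. Its reach is limited to lack of efficacy without qualifying clinical consequences, and it falls mainly on AE counts. The effect on SAE counts is probably small.

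The size cannot be fixed from the documents. The figure of 0.54 percentage points per subject assumes that all 186 are in the safety population and that the subject has no other AE. The 1% to 10% range is illustrative and has no source in the plan. The point should be corrected because the definition is operative and the correction is cheap. It does not call the trial's main results into question.

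**What to change.** 1. Reconcile the two paragraphs of Protocol 6.3.3.1 into one reporting rule. The sponsor must say which was meant, since the documents do not. Check that the Study Procedures Manual agrees.
2. State the same rule in SAP 7.5.1, including how it applies to virological breakthrough and unsatisfactory response without clinical sequelae.
3. Flag in the AE dataset any term reported solely as lack of efficacy or failure of drug effect, and present the AE summaries with and without the flagged terms. Sites may already have reported under either reading.
4. Cross-check the flagged terms against SAP Tables 4.9.1 and 4.9.3 and against the disposition reasons, so that a withdrawal appearing in both the disposition and the safety tables can be recognised.

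The cost is one clarified paragraph in the protocol, a matching sentence in the SAP, one dataset flag and a repeat run of the AE summaries. No new data collection is needed.
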